7.2.2.4 Incidence of Related Grade 3 AEs

After each study injection the Investigator or designee will record toxicity grade on the Adverse Event CRF.

The number (%) of subjects in each treatment group who experience at least one Grade 3 AE judged related to study injection during the study will be summarized. Brief narratives will be provided in the study report for each subject experiencing at least one Grade 3 AE.

7.2.2.5 Laboratory Data

Summaries of the actual value and change from baseline for all laboratory tests will be provided for each study visit. A tabulated summary of laboratory abnormalities by toxicity grade will also be provided.

7.2.2.6 Vital Signs

Summaries of the actual value and change from baseline for all vital signs will be provided for each study visit.

7.2.3 Immune Response

The following are the endpoints of interest:

Primary Analysis Endpoints:

- IgG antibody responses to ID93 by ELISA at Days 0, 14, 56, 70, 84, and 224
 - Mean endpoint titer of ID93-specific antibodies for total IgG on for each treatment group.
 - The proportion of subjects with at least a 4-fold increase in ID93-specific IgG antibody levels on Days 14, 56, 70, 84, and 224 relative to baseline (Day 0).
 - Mean fold change from baseline (Day 0) in IgG antibody responses to ID93.
- T cell responses to ID93 by PBMC ICS on Days 0, 7, 14, 56, 63, 70, 84, and 224
 - The proportion of cells expressing any two of IFN- γ , TNF, IL-2, IL-4, IL-21, or CD154 in response to ID93.
 - The polyfunctionality based on expression of IFN- γ , TNF, IL-2, IL-4, IL-21, or CD154.
- T cell responses to ID93 by ELISpot on Days 0, 14, 56, 70, 84 and 224
 - The number of IFN- γ cytokine-secreting cells in PBMC samples in response to the ID93 antigen relative to baseline (Day 0) at Days 14, 56, 70, 84, and 224, as assayed by ELISpot.

Secondary and Exploratory Analysis Endpoints:

- IgG subclass antibody responses to ID93 by ELISA at Days 0, 14, 56, 70, 84, and 224

- The proportion of subjects with at least a 4-fold increase in ID93-specific IgG1, IgG2, IgG3, and IgG4 antibody levels on Days 14, 56, 70, 84, and 224 relative to baseline (Day 0).
- Mean endpoint titer of ID93-specific antibodies for IgG1, IgG2, IgG3, and IgG4 on for each treatment group.

Immune responses for each treatment group will be evaluated by calculating the response rate and magnitude of response to ID93 at all timepoints for each immunologic endpoint. Comparisons of response rates for IgG and cytokine responses between treatment groups will be made using Fisher's exact tests.

The magnitude of IgG and cytokine responses will be compared between treatment groups using a Two-sample T-test if normality assumption is met or Wilcoxon Rank-Sum Test, otherwise.

Percentages of CD4+ cells producing selected immune markers will be summarized by time point and compared between treatment groups.

A boxplot with overlaid symbols (one per subject) will be used to summarize the magnitude of an immune response in a single group. Different colors and symbols will be used to indicate responders and non-responders. The boxplot will be used to summarize the responders with a horizontal line for the median, the extents of the box indicating the inter-quartile range (IQR) and whiskers indicating the lowest (highest) data point within 1.5 x IQR within the lower (upper) quartile.

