3.2.2 Secondary Outcome Measures

- The proportion of subjects with at least a 4-fold increase in IgG antibody responses to ID93 on Days 14, 56, 70, 84, and 224 relative to baseline (Day 0).
- Mean fold change from baseline (Day 0) in IgG antibody responses to ID93 on Days 14, 56, 70, 84, and 224.
- The number of IFN- γ and IL-10 cytokine-secreting cells in PBMC samples in response to the ID93 antigen relative to baseline (Day 0) at Days 14, 56, 70, 84, and 224, as assayed by ELISpot.
- Percentage of CD4 and CD8 T cells producing 1 or more cytokines (IFN- γ , TNF, and IL-2) simultaneously in response to stimulation with the ID93 antigen as measured by intracellular cytokine staining of PBMCs at Days 14, 56, 70, 84, and 224 relative to baseline (Day 0).

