11.5.3 Immunology Analyses

Immunogenicity will be assessed from blood samples obtained on Days 0, 7, 14, 56, 63, 70, 84, and 224. Secondary immunogenicity evaluations will include quantification of T cell cytokine responses from stimulated PBMCs and serum IgG antibody responses to ID93. Exploratory analyses will include measurement of functionality of immune responses through the whole blood mycobacterial growth inhibition assay (MGIA), measurement of humoral responses in mucosal secretions (nasal swabs and tears), quantitation of IgA and IgG secreting B cells and memory B cells, and measurement of the frequencies of peripheral T follicular helper cells, memory B cells, and T cell homing markers.

Immune responses for each treatment group will be evaluated by calculating the response rate and magnitude of response to ID93 at all timepoints for each immunologic endpoint. Comparisons of response rates for IgG and cytokine responses across treatment groups will be made using $n \times m$ Fisher's exact tests. Pairwise comparisons will be done using 2×2 Fisher's exact tests with multiplicity adjustment to control the family-wise error rate (FWER).

The magnitude of IgG and cytokine responses will be compared across treatment groups using ANOVA when the distribution is Gaussian and Kruskal-Wallis when the distribution is non-Gaussian. When ANOVA is used and a difference is observed across the treatment groups, pairwise comparisons will be made using t-tests with adjustment to control the FWER. If Kruskal-Wallis is used, Wilcoxon rank-sum tests will be used.

Percentages of CD4 and CD8 T cells producing selected cytokines will be summarized by time point and compared across and between treatment groups.

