1 INTRODUCTION

Note: The safety analysis has already been performed. This amendment is to the immunology section only.

The purpose and scope of this document is to describe the statistical analysis plan (SAP) that will guide the analysis of the clinical safety, IgG ELISA, ELISpot, and ICS data (primary and secondary study objectives and endpoints) for the final study report for protocol IDRI-TBVPX-120.

The clinical study report will be prepared after all study subjects have completed all study visits, all data in the clinical study database have been reviewed, all data queries have been resolved, the clinical database has been locked, and all immunology laboratory assays have been completed. All individual subject data listings, summary tables, and statistical analyses described below will be provided in separate appendices to the study report. Unless otherwise indicated, all listings and summary tables will be provided by treatment group.

This SAP is written with consideration of the recommendations outlined in the International Conference on Harmonization (ICH) E9 Guideline entitled Guidance for Industry: Statistical Principles for Clinical Trials¹ and the ICH E3 Guideline entitled Guidance for Industry: Structure and Content of Clinical Study Reports².

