7.2.3.2.1 ICS

PBMC ICS will be performed on Days 0, 7, 14, 56, 63, 70, 84, and 224 to determine the proportion of single and multi-functional CD4 and CD8 T-cells producing various combinations of IFN- γ , TNF, IL-2, IL-4, IL-21, and CD154 in response to ID93 stimulation. A gate is applied for each functional marker, not accounting for co-expression of other markers. Boolean gates are later created based on the gates shown to identify cells expressing various combinations of markers. We will analyze the T cell population “Any Two”, which are positive for at least two immune markers among IFN- γ , TNF, IL-2, IL-4, IL-21, and CD154. We will also evaluate T cells that express selected combinations of the six immune markers. The selected combinations will be indicated in the data set. Any negative background-subtracted values will be set to zero.

The following **listing** is planned to be presented:

- Cellular Response: PBMC ICS: T cell Response
 - Percent immune marker-positive (“Any Two” and for selected combinations of the six), background-subtracted cytokine response, change from baseline, fold change from baseline, and responder status

Tabular summaries will present “Any Two” immune marker-positive and polyfunctional responses (only background-subtracted non-zero values will be presented). T-cell response frequencies will be summarized by treatment regimen. Percentages will be based on the total number of subjects within each treatment group. The following **tables** are planned for presentation:

- Cellular Response: PBMC ICS: T cell Response and Change from Baseline
 - Percent immune marker-positive background-subtracted T cell response (“Any Two” and for selected combinations of the six) and change from Baseline, including N, Median, and 95% CI for each parameter.
- A Narrative Table will be prepared and will include
 - Medians of the “Any Two” CD4 and CD8 T cell responses per treatment group and study visit with p-value of the statistical comparison of the treatment groups

- Responder Rate of the “Any Two” CD4 and CD8 T cell responses per treatment group and study visit with p-value of the statistical comparison of the treatment groups

The following **figures** are planned:

- Cellular Response: PBMC ICS: T Cell Response Magnitude by Study Day
 - Background-subtracted total T cell subject response (“Any two”) by visit and by T cell type.

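### The SAP does not define or commit to the protocol's secondary ICS outcome (CD4 and CD8 T cells producing at least one of IFN-γ, TNF and IL-2); its named measure, any two of six markers, is not equivalent, and its selected combinations are not listed

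*SAP*

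**What the plan says.** **Protocol.** Section 3.2.2 lists a secondary outcome that opens "Percentage of CD4 and CD8 T cells producing 1 or more cytokines". The three cytokines it means are IL-2, TNF and IFN-γ, and the visits are Days 14, 56, 70, 84 and 224, each set against Day 0. The entry further requires that they be produced "simultaneously in response to stimulation with the ID93 antigen as measured by intracellular cytokine staining of PBMCs". Section 11.5.3 is looser about the analysis: "Percentages of CD4 and CD8 T cells producing selected cytokines will be summarized by time point and compared across and between treatment groups".

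**SAP scope.** Section 1 says the plan covers "IgG ELISA, ELISpot, and ICS data (primary and secondary study objectives and endpoints) for the final study report".

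**SAP endpoints.** Section 7.2.3 names two ICS endpoints, both under its primary immune-response heading:
- "The proportion of cells expressing any two of" six markers, namely the protocol's three cytokines plus IL-4, IL-21 and CD154. Section 7.2.3.2.1 calls this *Any Two* and makes clear that it means at least two of the six.
- Polyfunctionality based on the same six markers.

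**SAP ICS section.** Section 7.2.3.2.1 says the assay is run "to determine the proportion of single and multi-functional CD4 and CD8 T-cells producing various combinations of" the six markers. *Any Two* and certain combinations are then analysed. On the latter it says only: "The selected combinations will be indicated in the data set". The narrative table is to give medians and responder rates, with p-values, for *Any Two*.

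**SAP comparison rule.** For magnitude, section 7.2.3 says: "The magnitude of IgG and cytokine responses will be compared between treatment groups using a Two-sample T-test if normality assumption is met", and names the rank-sum test as the fallback. The section also plans a by-visit summary and group comparison of the percentage of CD4+ cells positive for selected immune markers. That sentence does not mention CD8 and names no markers.

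**The concern.** A plan that says it covers the secondary endpoints should let a reader trace each one from the protocol to a table. Here the trace breaks. No three-cytokine variable appears in the SAP's endpoint list, its ICS section, or the table, figure and listing titles in section 7.4. This does not look like shorthand: the same endpoint list carries over the protocol's 4-fold IgG, mean fold-change IgG and IFN-γ ELISpot measures almost unchanged.

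If the SAP is followed as written, the headline ICS comparison is made on a different variable. Whether the declared outcome is reported at all then depends on which combinations the data set contains. Comparing the immunogenicity of the two presentations is a secondary objective, and protocol 2.2 calls the trial a bridging study. What is at stake is the traceability of a declared outcome for that comparison.

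**Working it through.** The plan gives no figure to reproduce, so the check compares definitions. Each cell is positive or negative for each of six markers. IFN-γ, TNF and IL-2 come from protocol 3.2.2; IL-4, IL-21 and CD154 are added in SAP 7.2.3.

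1. Non-empty patterns: 2^6 − 1 = 63.
2. Protocol outcome, at least one of the three cytokines: 2^6 − 2^3 = 64 − 8 = **56**.
3. SAP *Any Two*, at least two of six: 63 − 6 single-marker patterns = **57**.
4. Protocol only: exactly one positive marker, and it is one of the three cytokines. This gives **3** patterns (IFN-γ alone, TNF alone, IL-2 alone).
5. Shared: 56 − 3 = **53**.
6. SAP only: 57 − 53 = **4**. These have none of the three cytokines and at least two of the added markers: IL-4+IL-21, IL-4+CD154, IL-21+CD154, and all three together.

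Neither set contains the other. Before background subtraction, the protocol percentage minus the *Any Two* percentage equals the cells in the 3 patterns of step 4 minus the cells in the 4 patterns of step 6. The sign can go either way, and the documents give no cell frequencies with which to size it.

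The protocol's wording joins 1 or more with simultaneously, so other readings need checking.

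- **At least two of the three cytokines.** Patterns: (3 + 1) × 2^3 = **32**, all inside *Any Two*. *Any Two* adds 57 − 32 = **25**. Of these, 3 × (2^3 − 1) = 21 have exactly one of the three cytokines plus an added marker, and 4 have none of the three.
- **A profile of each three-cytokine combination.** There are 2^3 − 1 = 7 combinations per cell type. The nearest SAP text is polyfunctionality on six markers through the selected combinations, and those are not listed.

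Under none of the three readings does the SAP's named measure equal the protocol's.

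**The case against.** The best case for the SAP is that it leaves room for the declared outcome.

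- Section 7.2.3.2.1 speaks of single as well as multi-functional CD4 and CD8 cells, and combination plots are planned for both cell types.
- Section 7.2.3 has the further sentence on CD4+ marker percentages compared between groups. This carries the protocol's own 11.5.3 sentence forward in part, and that sentence is no more specific about markers.
- The general comparison rule covers the endpoints the SAP lists, so polyfunctionality does have a between-group test.
- Under the profile reading, the SAP's approach is a recognisable, broader version of the outcome.

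All of this stands as far as it goes. It shows that the outcome is not ruled out, and that the CD4+ sentence is a partial commitment. It does not supply a defined three-cytokine variable, CD8 is missing from that sentence, and 11.5.3 does not withdraw the explicit definition in 3.2.2.

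A reader might go further and infer the following, which the documents do not support:

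- *The outcome can be rebuilt only if all 56 patterns (or 32, on the co-expression reading) are among those selected.* *Any Two* is itself a planned output. For the first reading, *Any Two* minus 4 patterns plus 3 single-positive patterns gives 57 − 4 + 3 = 56, so seven patterns would do. For the second, *Any Two* minus 25 gives the 32.
- *Setting negative background-subtracted values to zero must inflate any rebuilt value.* That holds for direct summing of combinations. By subtraction from *Any Two* the error can go the other way. In any case the analyst can gate directly.
- *Seven combinations, two cell types and five visits make 70 omitted results.* That turns one unlisted set into 70 separate omissions.
- *The open list points to selective reporting.* Protocol 8.2.2 places the ICS assay at IDRI, and 5.4.2 blinds the immunology laboratory staff. SAP section 6 has IDRI hold the assay data and transfer them before analysis. The natural inference is that combinations are chosen within the laboratory data, although no passage I have seen says who chooses or when.

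**Conclusion.** The point holds. The protocol's secondary ICS outcome is neither defined nor committed to in the SAP, the measure given p-values in the ICS narrative tables is a different one, and the combinations that might capture the outcome are unlisted. The mismatch is 56 against 57 patterns with 53 shared on the plain reading. On the co-expression reading it is 32 against 57. These are counts of marker patterns, not of cells, so the effect on any reported percentage or group difference is unknown.

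Two limits apply. Protocol 11.3 says the study is not designed to test a formal hypothesis, and the sample size was not based on power. The harm is therefore to traceability, and no claim about type I error follows. Also, I have not seen the SAP's front pages, so I do not say whether a reason for the change is recorded there. It should be fixed, because the declared outcome can otherwise go unreported while the plan is followed to the letter.

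**What to change.** In SAP 7.2.3, 7.2.3.2.1, Tables 14.3.2 and 14.3.3, and the ICS narrative tables:

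- Add the protocol-defined three-cytokine outcome for CD4 and for CD8 at Days 14, 56, 70, 84 and 224 relative to Day 0, derived from its own Boolean gate.
- Apply the between-group comparison already specified in 7.2.3.
- State how simultaneously is read.
- Keep *Any Two* as an additional analysis, labelled as not in the protocol.
- List the selected combinations before ICS data are merged with treatment codes. If that merge has already happened, label them post hoc.

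The cost is SAP wording, one more Boolean gate built from the per-marker gates already applied, and some added table rows. The SAP already schedules ICS at all five protocol visits and Day 0, so no new samples or assays are needed.

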7.2.3.1 IgG Antibody Response to ID93

IgG antibody responses (Total IgG, IgG1, IgG2, IgG3, and IgG4) to the ID93 antigen will be measured by ELISA using serum collected from a given subject. Specimens from all time points for a given subject will be analyzed on a single ELISA plate. The plate will contain standards and controls that will be used to determine plate validity based on criteria established during assay validation.

At each timepoint, the IgG mean endpoint titer (**Total IgG MEPT**) value calculated from duplicates or triplicates will be reported.

At each post-injection timepoint, the following **Post:Pre Ratio** will be calculated:

$$\text{Post:Pre Ratio} = \frac{\text{MEPT (Post-Injection Timepoint)}}{\text{MEPT (Baseline Timepoint)}}$$

A subject will be considered an antibody positive **Responder** at a given timepoint if:

- a) System suitability criteria for a given ELISA are met; and
- b) The Post:Pre Ratio at that timepoint is ≥ 4 .

The following **listing** is planned:

- Humoral Response: IgG ELISA: IgG Antibody Response

- This listing will be organized by treatment group and will include: Subject ID, Visit Day, Collection Date, IgG MEPT, Post:Pre Ratio, Responder (Yes/No)

The following **tables** are planned:

- Humoral Response: IgG ELISA: IgG Antibody Response
 - This is a tabulation by Visit Day of the Total IgG MEPT, Post:Pre Ratio, and Responder status of each treatment group. The table will include descriptive statistics and a statistical comparison of each parameter between the two treatment groups.
- A Narrative Table will be prepared and will include
 - Percent responder status at each time point with p-value of the statistical comparison of the treatment groups

The following **figure** is planned:

- Humoral Response: IgG ELISA: IgG Antibody Response
 - IgG MEPT (log10) by study visit and treatment group.
 - Repeated for each IgG subclass
 - This will be a line plot with error bars representing +/- 95% CI.

7.2.3.2 T-cell Responses to ID93

PBMC samples will be assayed by ICS and ELISpot.

7.2.3.2.1 ICS

PBMC ICS will be performed on Days 0, 7, 14, 56, 63, 70, 84, and 224 to determine the proportion of single and multi-functional CD4 and CD8 T-cells producing various combinations of IFN- γ , TNF, IL-2, IL-4, IL-21, and CD154 in response to ID93 stimulation. A gate is applied for each functional marker, not accounting for co-expression of other markers. Boolean gates are later created based on the gates shown to identify cells expressing various combinations of markers. We will analyze the T cell population “Any Two”, which are positive for at least two immune markers among IFN- γ , TNF, IL-2, IL-4, IL-21, and CD154. We will also evaluate T cells that express selected combinations of the six immune markers. The selected combinations will be indicated in the data set. Any negative background-subtracted values will be set to zero.

The following **listing** is planned to be presented:

- Cellular Response: PBMC ICS: T cell Response
 - Percent immune marker-positive (“Any Two” and for selected combinations of the six), background-subtracted cytokine response, change from baseline, fold change from baseline, and responder status

Tabular summaries will present “Any Two” immune marker-positive and polyfunctional responses (only background-subtracted non-zero values will be presented). T-cell response frequencies will be summarized by treatment regimen. Percentages will be based on the total number of subjects within each treatment group. The following **tables** are planned for presentation:

- Cellular Response: PBMC ICS: T cell Response and Change from Baseline
 - Percent immune marker-positive background-subtracted T cell response (“Any Two” and for selected combinations of the six) and change from Baseline, including N, Median, and 95% CI for each parameter.
- A Narrative Table will be prepared and will include
 - Medians of the “Any Two” CD4 and CD8 T cell responses per treatment group and study visit with p-value of the statistical comparison of the treatment groups

- Responder Rate of the “Any Two” CD4 and CD8 T cell responses per treatment group and study visit with p-value of the statistical comparison of the treatment groups

The following **figures** are planned:

- Cellular Response: PBMC ICS: T Cell Response Magnitude by Study Day
 - Background-subtracted total T cell subject response (“Any two”) by visit and by T cell type.
 - This figure is also to include on separate pages the DMSO values as well to illustrate background for T cell results.
 - This is to be a **box and dot plot** of the background-subtracted with negative values set equal to zero ‘Any two’ with background-subtracted (or background values) values (y-axis) at each visit (x-axis) (study days plotted next to each other on one page). Box plots summarize by treatment group and dots represent individual values. The median values per treatment group are to be presented by means of a horizontal line, boxes outline first to third quartiles, and whiskers represent minimum to maximum values.
 - Different symbols are to be used to differentiate between responders (closed circles), non-responders (cross) and missing responder status (triangle).
- Cellular Response: PBMC ICS: Polyfunctional Profile Plot in CD4 and CD8 T Cells
 - Background-subtracted polyfunctional plot in T cells (selected combinations of IFN- γ , TNF, IL-2, IL-4, IL-21, and CD154) by visit and T cell type.
 - Separate pages for each visit day are to be prepared.
 - This is to be a **dot plot** of the background-subtracted single-gate T cell response (y-axis) versus each selected immune marker combination available (excluding where all included cytokines are negative) (x-axis).
 - The background-subtracted ANY TWO cytokine response in T cells is to be presented as a subplot on the right hand side.

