7.2 Plan for Statistical Summaries and Analyses

7.2.1 General Considerations

Statistical summaries and analyses of baseline and safety data will be provided for the safety population, defined as all subjects who receive at least one study injection. Summaries and analyses of immune response data will be provided for the per-protocol population. The objectives of the immune response statistical summaries and analyses are to assess the immunogenicity following intramuscular administration of study vaccine among the treatment groups. The goals are:

1. To describe the humoral and cellular response to both vaccine presentations in terms of magnitude and positive response rate
2. To determine if there is a significant difference in the immune response elicited by the two-vial and the single-vial lyophilized vaccine presentation

All individual subject data listings will be provided in appendices to the clinical study report. Data will be summarized and tabulated by treatment group and descriptive statistics will be provided where

appropriate. The immunology analysis will be performed using either SAS version 9.3 or higher or R version 3.5 or higher.

Categorical data will be analyzed using Fisher's exact test using 0.05 level of significance ($\alpha = 0.05$) with Holm-Bonferroni adjustments whenever pairwise comparisons are made between more than two categories.

Continuous data will be compared between two treatment groups using a Two-sample T-test if the normality assumption is met or Wilcoxon Rank-Sum Test, otherwise. Response rates will be compared using a Fisher's Exact test. Significant differences will be detected based on a two-sided test with $p \leq 0.05$ ($\alpha = 0.05$). Comparisons will be accompanied by the point-estimate and 95% CI for each group.

Missing data: The analysis plan assumes that missing data are missing completely at random (MCAR) and analysis will be performed on the available data.

Individual subject data listings will be provided as separate appendices in the CSR. All summaries, statistical analyses, and individual subject data listings will be analyzed by using either SAS version 9.3 or higher or R version 3.5 or higher.

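### As written, the ICS tables drop subjects whose background-subtracted response is zero, so response medians can be too high and can disagree with the ICS box plot

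*SAP*

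**What the plan says.** SAP 7.2.3.2.1 gives two rules for ICS values. The first is a floor: "Any negative background-subtracted values will be set to zero". The second introduces the tabular summaries of the Any Two and polyfunctional responses and adds in brackets that "only background-subtracted non-zero values will be presented". The tables that follow report N, median and 95% CI for the response and for its change from baseline. A narrative table is also to show the Any Two medians, described as "CD4 and CD8 T cell responses per treatment group and study visit with p-value of the statistical comparison of the treatment groups".

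Between the bracket and the table list, the same section bases percentages on every subject in the treatment group. That sentence covers response frequencies. It does not mention medians.

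The figure instructions in the same section differ from the table rule. The Any Two figure is a box and dot plot "of the background-subtracted with negative values set equal to zero", with whiskers from minimum to maximum, and "Box plots summarize by treatment group and dots represent individual values".

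The test is defined in general terms. SAP 7.2.3 says: "The magnitude of IgG and cytokine responses will be compared between treatment groups using a Two-sample T-test if normality assumption is met", with the Wilcoxon rank-sum test otherwise. SAP 7.2.1 uses the per-protocol population for immune data and says, as its missing-data rule, that "analysis will be performed on the available data". Neither section excludes zeros.

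**The concern.** A floored zero is an observed result: the assay was valid and showed nothing above background. It is not missing, so the missing-data rule gives no reason to drop it. A table restricted to non-zero values selects subjects on the outcome being summarised, and it removes only the weakest responses.

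Two things are at stake. First, the medians and intervals by arm and visit would describe only subjects with a positive value, without being labelled that way. Second, the planned outputs could disagree: the box plot keeps the zeros and the table does not, so one endpoint at one visit in one arm could have two medians. SAP 7.2.3 places the Any Two response among its primary immune analysis endpoints, and SAP 7.2.1 makes a comparison of the two presentations an explicit goal. If one presentation produced more zeros, the tabulated medians would understate that.

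**Working it through.** The SAP states no ICS figure, so there is nothing to reproduce. The share of zeros and the spread of the positive values are assumptions throughout. Group sizes of 25 and 23 are from SAP Table 1 and are upper limits for the per-protocol population.

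**1. Direction.** Zero is the smallest possible floored value, so removing zeros cannot lower a response median. Example: 25 subjects, 6 zeros, the other 19 at 0.01, 0.02, …, 0.19. With zeros the median is the 13th value, which is the 7th positive: 0.07 (N = 25). Without zeros it is the 10th of 19: 0.10 (N = 19).

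**2. Size.** Let p be the share of zeros and s the log10 SD of lognormal positive values. The all-subject median is the q-quantile of the positives, with q = (0.5 − p)/(1 − p). The tabulated median divided by the all-subject median is therefore 10^(−s·z(q)), where z is the standard normal quantile. At p = 0.20, q = 0.375 and z = −0.319; with s = 0.5 the ratio is 10^0.159 = 1.44.

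| Zeros | q | z(q) | s = 0.3 | s = 0.5 | s = 0.7 |
|---|---|---|---|---|---|
| 0% | 0.500 | 0 | 1.00 | 1.00 | 1.00 |
| 10% | 0.444 | −0.140 | 1.10 | 1.17 | 1.25 |
| 20% | 0.375 | −0.319 | 1.25 | 1.44 | 1.67 |
| 30% | 0.286 | −0.566 | 1.48 | 1.92 | 2.49 |
| 40% | 0.167 | −0.967 | 1.95 | 3.05 | 4.76 |

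Above 50% zeros the all-subject median is zero and the table would still show a positive number.

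**3. Where it matters.** Take normal values with SD 1 (in noise units), floored at zero, 25 subjects. With no true response the average median is 0.10 on all values and 0.69 on non-zero values, about 12 of 25 subjects being kept. With a true mean of 2 (2% zeros) the two are 2.00 and 2.03. Strong responses are barely affected; responses near background, such as those at Day 0, are.

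**4. Confidence interval.** For s = 0.5, 25 subjects and an order-statistic interval (assumed, since the SAP names no method), a nominal 95% CI from non-zero values covers the all-subject median in 95, 86, 64 and 29% of samples at 10, 20, 30 and 40% zeros. On all values it covers 95 to 96%.

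**5. Change from baseline.** The direction is not fixed. Take Day 0 values with mean 0 and post-dose values with mean 2, both with SD 1 and floored, 24 subjects. The average median change is 1.64 on all values, 1.26 if both values must be non-zero, and 1.67 if only the post-dose value must be.

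**6. Medians against the p-value.** Suppose the Wilcoxon test keeps zeros and the medians do not (25 v 23 subjects, two-sided 0.05). Two models were run. In A, the arms differ only in the share of zeros and have the same lognormal positives (s = 0.5). In B, zeros arise by flooring a normal distribution with SD 1 and mean −z(p); for example 5% v 30% zeros means 1.64 v 0.52. The entries are percentages of significant results, with the range over repeat runs where they differed.

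| Zeros by arm | A: tabulated medians reversed | A: within 25% | B: reversed | B: within 25% |
|---|---|---|---|---|
| 5% v 30% | 17 to 20 | 29 to 31 | 0.4 to 0.5 | 5 |
| 10% v 40% | 26 to 28 | 33 to 34 | 1.4 to 2 | 9 |

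At 10% v 20% few results are significant under A (9%), and the reversal share is too unstable to rely on (2 to 6% over repeat runs). With zeros kept in the medians, no significant result was reversed under A in any of the three settings.

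**The case against.** The strongest reply is that the bracket may not mean what it says. *Non-zero* could be a slip for *non-negative*, which would only restate the floor. It could also be a display rule for marker combinations, like the one for the polyfunctional plot, which omits combinations by "excluding where all included cytokines are negative". Under either reading no subject leaves the Any Two medians. Basing percentages on all subjects lends some support to the display reading. This stands as an open question. The text does not settle it, and either reading still needs a wording correction.

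Second, a reader might infer that the SAP prescribes medians and a p-value from different sets of subjects. The documents do not go that far. The test rules in 7.2.1 and 7.2.3 are general, the available-data sentence concerns missing values, and the test set for the ICS narrative table is never restated. The mismatch is an inference from the absence of any stated exclusion. If the test were filtered as well, it would match the table but would compare groups selected on their own response.

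Third, a reader might infer that medians reversed beside a significant p-value would be common. That depends on model A. The SAP's zeros come from flooring, and under a shifted, floored distribution (model B) the arm with more zeros also has lower positive values, so reversals are rare. This objection stands.

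Fourth, there are safeguards. N is tabulated, no filter is stated for the listing, the figure shows every subject, and a responder-rate comparison is planned. These let a careful reader notice the exclusion, but they do not correct the printed median or interval. One could also point to the general boxplot rule in SAP 7.2.3, which summarises responders, as a precedent for positive-only summaries. The ICS figure has its own instruction, which keeps the zeros, and I read that as governing.

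**Conclusion.** The concern holds in a limited form. Read as written, the rule removes observed subjects because of their outcome, so response-level ICS medians are equal or too high wherever zeros occur, and change from baseline can be distorted in either direction. For lognormal positives with log10 SD 0.5 the factor is 1.17 at 10% zeros, 1.44 at 20% and 3.05 at 40%; with no zeros nothing changes. The true share of zeros is not in the documents. The conflict between table and box plot follows directly from SAP 7.2.3.2.1 under that reading. The conflict between medians and p-value is only inferred.

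Response frequencies are protected by the all-subjects denominator; medians are not. Reversed or look-alike medians beside a significant result are possible, but how often depends on the model: about 17 to 28% of significant results are reversed if the arms differ only in the share of zeros, and about 0.4 to 2% if zeros come from flooring a shifted distribution.

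The stakes are modest. ICS is a secondary outcome in Protocol 3.2.2, and Protocol 11.3 says that no formal hypothesis is tested. It is worth fixing because the correction is small.

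**What to change.** Delete the bracketed restriction in SAP 7.2.3.2.1. If *non-negative* or a marker-combination display rule was meant, say so instead. State that N, median, 95% CI, change from baseline and the group comparison all use every per-protocol subject with a valid ICS result at that visit, zeros included, to match the box plot in the same section. Add the number of zeros by arm and visit to the table. If a positive-only summary is wanted, show it beside the all-subject result, labelled as supplementary and conditional on a value above zero.

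The cost is a sentence of SAP text and one data filter, with no new data. The downside is cosmetic: medians will look lower wherever zeros occur, and will be zero where more than half the values are zero.
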